## 9.4 Safety Analysis

Descriptive methods will be used for analysis of safety parameters, adverse events and their intensity in total and reported separately for the intervention groups. Incidence rates and 95% confidence intervals (CI) will be calculated using Poisson regression models that consider the different observation periods for each participant. Group comparisons will be made using incidence rate ratios and their 95% CIs. The safety analysis results will be carefully interpreted and discussed, even for minor group differences, as statistical significance is not the main focus in this context. A comprehensive listing of all individual patient adverse events (AEs) and severe adverse events (SAEs) will be presented. This will include, for each event, the patient identifier, treatment arm, AE/SAE term (coded using Medical Dictionary for Regulatory Activities [MedDRA]), verbatim term, onset date, resolution date, severity (e.g., mild, moderate, severe), seriousness criteria (if applicable), causality assessment (e.g., related, not related to study drug), action taken with study drug, and outcome. Separate listings will be generated for AEs and SAEs. Furthermore, any AEs leading to study drug discontinuation or study withdrawal will be specifically highlighted. These listings will serve as a detailed and transparent record for safety monitoring and will facilitate thorough review by medical monitors and regulatory authorities.

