## 4 Trial design

This is a double-blinded, randomized, sham-controlled post-marketing (exploratory) trial to evaluate the therapeutic effect of five cycles of immunoabsorption every other day in 66 patients with CFS/ME, including patients with PACS-CFS. Two patient groups will be included (2:1), one receiving IA, one receiving a sham-apheresis.

A screening visit is planned up to max. 3 weeks (Day -42 to Day -21) before enrolment in the study to screen patients for eligibility (including blood and urine samples for safety parameters such as viral serology, pregnancy, drug and alcohol tests) and to assess demographics and medical history (table 1). In addition, cerebrospinal fluid and blood samples are taken to test for autoantibodies and markers of neurodegeneration or neuroinflammation. If a lumbar puncture was performed as part of the clinical routine within 6 months prior to the screening visit, it will not be repeated at screening. Patient reported outcome measurements such as Chalder Fatigue Scale, physical and autonomic function, quality of life and (in case of PACS-CFS) Post-COVID-19 Functional Status Scale questionnaires as well as Cognitive (MoCA and SDMT), physical (hand grip strength evaluation, 6MWT), and autonomic (Schellong-Test) assessments are performed at

screening or baseline visit. At baseline visit a detailed neuropsychological examination, and an assessment of physical function will be conducted.

Baseline assessments will be performed between Day -20 and -1 and in any case before the first IA cycle. These include a general and neurological physical examination assessing vital signs, ECG, body weight, repeating safety check for pregnancy. Blood samples for chemistry, hematology, coagulation and immunoglobulin titers are taken.

Patients are randomized either on Day -1 or Day 1 and a peripheral venous access (or Shaldon catheter) is implemented before the first IA cycle on Day 1 or Day 2 (Figure 1). Patients will be hospitalized at the clinical site from Day 1 to Day 9 or Day 10 and receive five IA treatments and medical visits including monitoring of coagulation every other day (i.e., on Days 1, 3, 5, 7, and 9 OR on Days 2, 4, 6, 8, and 10). If delays occur, the option to extend the in-hospital stay is available. Immunoabsorption can be postponed by one or more days.. Daily study nurse visits are scheduled including control of vital signs as well as questioning for AE(s).

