After the last IA cycle, a blood sample for immunoglobulin titers is collected, the peripheral venous access (or Shaldon catheter) is removed and patients are discharged from the hospital if the investigator has no concerns. At EOT visit, patients will also complete the Chalder Fatigue Scale (Chalder et al., 1993), Fluge Score (Fluge et al., 2011; Fluge et al., 2015), and PEM questionnaires. In addition, patients will be instructed how to complete all of the requested questionnaires at home at follow up time points. If the IA treatments are performed according to the planned schedule, the end of treatment visit (EOT) will take place on Day 10. However, the EOT visit may vary between Day 9 and 12. If treatment needs to be terminated, the EOT can occur as early as day 2. In such cases, all examinations originally scheduled for day 10 will be conducted on the corresponding day. In addition, two of the four follow-up visits scheduled at month 2 (Day 60) and month 6 (Day 180; EOS, End of Study visit) will take place at the neurological wards and outpatient clinics respectively. Patients will be asked to bring all requested questionnaires (including Chalder Fatigue Scale), which they completed at home, to both follow-up visits, where further assessments and laboratory tests will be conducted. An optional second cerebrospinal fluid sample may also be taken on Day 60. The remaining two follow-up visits, scheduled at month 1 (Day 30) and month 4 (Day 120), will be conducted via telephone. During these visits, patients will be asked about any adverse events (AEs), concomitant medications, and questionnaires.

Figure 1 Schematic illustration of the study design

[figure not shown]

Table 1: Schedule of Assessments

| Period/Visit name  | SCR               | BL  | Treatment period (inpatient) |                 |                 |                 |                 |                 |                 |                 |     | Follow-up |                   |                  | EOS                |                         |
|--|-------------------|------------------|------------------------------|-----------------|-----------------|-----------------|-----------------|-----------------|-----------------|-----------------|-----|-----------|-------------------|------------------|--------------------|-------------------------|

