## 7.3 Secondary variables

### Safety related endpoints:

Occurrence of treatment emergent adverse events (TEAEs), serious adverse events (SAEs), and discontinuation due to TEAEs

Assessment of physical examinations, laboratory parameters, vital signs, and ECGs

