| inflammatory biomarkers in serum and cerebrospinal fluid (white cell count, total protein, CSF/serum quotients of albumin (Qalb), lactate, oligoclonal IgG bands (OCB), cytokines))  | haem_0051-haem_0273, chem_0011-chem_0083, liq_0011-liq_0173  |  |
| MRI measures: grey matter volume, white matter volume, thalamus volume left and right, thalamic functional connectivity to sensomotoric cluster left and right, thalamic functional connectivity to visuo-occipital cluster left and right, EndoPAT Reactive Hyperemia Index (RHI) | gm_volume, wm_volume, thalamus_l_volume, thalamus_r_volume, thalamic_motor_l_fc, thalamic_motor_r_fc, thalamic_occipital_l_fc, thalamic_occipital_r_fc, endopat_rhi  |  |
| OCT: ganglion cell-inner plexiform layer (GCIPL), peripapillary retinal nerve fiber layer (pRNFL), foveal avascular zone (FAZ), vessel density   | gcipl, prnfl, faz, vessel_density_full   |  |
| CD11c Expressions (CD19+ B cells, IgD-CD27+ memory B cells), IgM Expressions, Activated canonical class-switched memory B cells  | z_cd11c_exp_cd19pl, z_cd11c_exp_igdmin_cd27plus_cd19pl, perc_cd11cpl_cd19pl, perc_cd11cpl_igdmin_cd27pl_cd19pl, z_igm_exp_cd19pl, z_igm_exp_igdmin_cd27pl_cd19pl, perc_igmpl_cd19pl, perc_igmpl_igdmin_cd27pl_cd19pl, perc_acsm_igdmin_igmmmin_cd27pl_cd11cmin_cd19pl, perc_cl_acsm_igdmin_cd27pl_cd19pl |  |
| Safety related endpoints   |  |  |

|  |                   |  |
|--|-------------------|--|
| Adverse events and severe adverse events | ae_0053, sae_0123 |  |
|--|-------------------|--|

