### 9.3 Secondary analyses

For all secondary endpoints, descriptive statistics will be calculated and presented at each time point of measurement for both treatment groups. For continuous secondary outcomes, this will include the mean, standard deviation, median, interquartile range, minimum, and maximum. For categorical or ordinal secondary outcomes, frequencies and percentages will be reported. These descriptive summaries will be presented in tabular format, and appropriate graphical representations, such as line plots for longitudinal data, bar charts, or box plots, will be utilized to visually depict trends, distributions, and differences between treatment arms across all assessment time points. For all secondary endpoints, analysis of

covariance (ANCOVA) models will be employed, analogous to the approach for the primary outcome. The choice of link function will be tailored to the specific nature of each outcome variable (e.g., linear for continuous outcomes, binary logistic for dichotomous outcomes, or ordinal for ordered categorical outcomes). In instances of repeated measures, mixed-effects regression models will be utilized, incorporating random intercepts for individual participants to account for within-subject correlation. Each model will include the respective baseline value of the endpoint, age at baseline, and treatment group as fixed effects. Effect estimates for the treatment variable, along with their 95% confidence intervals (CI), will be reported. All analyses will be conducted using the Full Analysis Set (FAS). Sensitivity analyses will be performed using the Per-Protocol Set (PPS), without imputation of missing values, to assess the robustness of the findings.

**Responder analysis:** Explorative analyses comparing responders and non-responders in both groups regarding PCS-associated signature at baseline: CD11c and IgM expression and an aCSM frequency. For this analysis a binary logistic regression model will be implemented with the responder (yes/no) variable as the dependent variable, the PCS-associated signature at baseline, the group and the interaction term between PCS-signature at baseline and group as independent variables.

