## 11 Software

R (version 4.4.2 or later) will be used. For multiple imputation of missing values, the package mice will be used (van Buuren and Groothuis-Oudshoorn (2011)). For mixed models, the R package lme4 will be used (Bates et al. (2015)). For marginal mean estimates, the R package emmeans will be used (Lenth (2024)).

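### Section 9.4: Poisson confidence intervals for adverse event rates and rate ratios would be too narrow if all events are counted and patients differ in how prone they are to events

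*SAP*

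**What the plan says.** Section 9.4 sets the model for AEs: "Incidence rates and 95% confidence intervals (CI) will be calculated using Poisson regression models that consider the different observation periods for each participant". For IA versus sham it adds: "Group comparisons will be made using incidence rate ratios and their 95% CIs". It names no variance estimator and no allowance for several events in one patient.

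What is counted is not fixed elsewhere. Section 7.3 gives the endpoint as "Occurrence of treatment emergent adverse events (TEAEs), serious adverse events (SAEs), and discontinuation due to TEAEs", and the safety row of Table 5 reads "Adverse events and severe adverse events" with nothing in the values column.

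Section 4 shows that AEs are collected repeatedly. A study nurse asks about them daily in hospital, and of the telephone contacts at months 1 and 4 the SAP says: "During these visits, patients will be asked about any adverse events (AEs), concomitant medications, and questionnaires". Observation runs to Day 180.

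**The concern.** A Poisson model with observation time as its only adjustment takes the variance of a patient's event count to equal its mean. That fails when some patients report many events and others few. Events then cluster within patients, and the total in each arm varies more between repetitions of the trial than the model allows. The standard error of the log rate ratio is too small and the interval too narrow.

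The interval is the only planned measure of uncertainty for the comparison of AE rates, and section 9.4 says that even small group differences will be discussed. With 22 sham patients, a few event-prone people could produce a difference that looks more precisely estimated than it is. A ratio near 1 could equally look more reassuring than the data justify.

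**Working it through.** The SAP gives no rate or precision figure for AEs, so there is none of its own to reproduce.

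**Inputs.** From the SAP: 44 and 22 patients (section 4.2), 95% intervals from Poisson regression (section 9.4), and 20% drop-out (section 4.2) for a robustness check. Assumed: mean μ AEs per patient, and patient-specific rates with mean 1 and variance k relative to the average. k = 0.25 means a between-patient SD of 50% of the mean rate, and k = 1 an SD of 100%.

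**Formulas.** With Y₁ and Y₀ events and equal follow-up, the model-based SE of the log rate ratio is √(1/Y₁ + 1/Y₀). If rates vary between patients, a count has variance μ(1 + kμ), so the true SE is larger by √(1 + kμ). Approximate coverage is P(|Z| < 1.96/√(1 + kμ)).

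**One case by hand.** Take μ = 2 and k = 0.5:
- Expected events are 88 and 44, and the model SE is √(1/88 + 1/44) = 0.185. The interval is the ratio multiplied or divided by exp(1.96 × 0.185) = 1.44.
- The true SE is 0.185 × √2 = 0.261, so the factor should be exp(1.96 × 0.261) = 1.67.
- Approximate coverage is P(|Z| < 1.386), about 83%. Simulation gives 83.6%.

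**Simulated coverage of the nominal 95% Poisson interval for the rate ratio** (all events counted, true ratio 1, equal follow-up, gamma-Poisson counts, 40,000 trials per setting):

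| Mean AEs per patient | k = 0 | k = 0.25 | k = 0.5 | k = 1 |
|---|---|---|---|---|
| 0.2 | 97.3% | 96.9% | 96.5% | 96.0% |
| 0.5 | 95.7% | 94.4% | 93.1% | 90.3% |
| 1 | 95.2% | 92.3% | 89.8% | 83.9% |
| 2 | 95.2% | 89.1% | 83.6% | 74.9% |
| 4 | 95.2% | 83.7% | 74.5% | 62.0% |

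A separate run of 20,000 trials per setting agreed where the settings overlap (89.5% at mean 2, k 0.25) and gave 98.0% to 98.4% at mean 0.1. Intervals for the rate in a single arm behave alike: 85% to 93%, 75% to 91% and 63% to 84% at means 1, 2 and 4. Trials with no event in one arm are excluded from coverage. They make up 1% to 2% at mean 0.2 and 12% to 14% at mean 0.1.

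**Alternatives.** Quasi-Poisson with the scale held at 1 or above and a t quantile on 64 degrees of freedom covers 94.9% to 96.2% at means 0.5 to 4 with k above 0, and about 96% at k = 0. With 20% drop-out and true ratios of 1 and 1.5 (means 1 to 4), quasi-Poisson covers 94.2% to 96.5% and a patient-level robust variance with t quantile 93.0% to 94.8%.

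**What the change does to an interval** (observed ratio 1.0, k = 0.5):
- Mean 1: Poisson 0.60 to 1.67, quasi-Poisson 0.53 to 1.89.
- Mean 4: Poisson 0.77 to 1.29, quasi-Poisson 0.64 to 1.57.

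**The counting rule changes the estimate too.** Take k = 1, means 2 (sham) and 3 (IA), true ratio 1.5, follow-up scaled to 1:
- All events: 3/2 = 1.5.
- First event per time at risk: the probability of an event is μ/(1 + μ) and mean time at risk is ln(1 + μ)/μ. The rates are 0.667/0.549 = 1.21 and 0.75/0.462 = 1.62, a ratio of 1.34.
- Each patient once over full follow-up: 0.75/0.667 = 1.13.

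**The case against.** Three conditions must hold together before the intervals are too narrow: all events counted, model-based variance, and real differences between patients. The SAP establishes none of them. Naming Poisson regression does not rule out a scaled or robust variance. If only first events per time at risk are counted, the planned interval covers 94% to 97% at means of 0.2 to 1 and 89% to 95% at mean 4. Section 9.4 also says that significance is not the main focus, the methods are called descriptive, the trial is labelled exploratory, and the patient-level listings would reveal a difference driven by a few people. All of this stands. It makes the point conditional and small, but it does not make the described interval a good default for repeated events.

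A reader might infer more than the SAP supports:
- *That section 11 shows the model-based variance will be used.* It does not. A Poisson or quasi-Poisson model needs no extra R package, so a list naming packages for other tasks is no evidence either way.
- *That the planned sentence may equally give intervals that are too wide.* This would require counting each patient once over full follow-up, a strained reading of incidence rates adjusted for individual observation time.
- *That the Poisson model is unsuitable for serious adverse events.* Coverage is 96% to 98% at means of 0.1 to 0.2. Arms with no events are a separate matter.
- *That only the interval is affected.* This is true of the variance choice. The counting rule, as shown, moves the rate and the ratio as well.

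**Conclusion.** The point holds in conditional form, as a cheap improvement. If total AEs are analysed with the model-based Poisson variance and patients differ in proneness, nominal 95% intervals cover about 84% to 92% at a mean of 1 AE per patient, 75% to 90% at 2 and 62% to 84% at 4 (k from 1 to 0.25). There is no loss without heterogeneity, and none at means of 0.1 to 0.2. Both the AE frequency and k are assumptions, so the actual loss cannot be read from the SAP. It would be wrong to conclude that the trial's safety intervals will be misleading. The unstated numerator is mostly missing detail, and matters here because the right variance depends on it. No decision rule uses these intervals.

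**What to change.** Add to section 9.4, in substance:

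> Total AEs are analysed as counts of all events, with log observation time as offset. The 95% CIs for rates and rate ratios use a variance that allows for repeated events within a patient (quasi-Poisson with scale not below 1, or a patient-level robust variance), with a t quantile. The number and percentage of patients with at least one AE and at least one SAE are shown by arm.

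Choose one of the two variances before the data are analysed. Quasi-Poisson had slightly better coverage at this sample size, but either is acceptable. The rule in section 9.3, "For categorical or ordinal secondary outcomes, frequencies and percentages will be reported", may already be meant to cover the patient percentages; section 9.4 should then say so. The planned rate model for SAEs need not change.

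The cost is a few sentences and a small amount of R code, since R's quasi-Poisson family does not hold the scale at 1 by itself. When patients differ, total-AE intervals widen on the log scale by √(1 + kμ), from √1.25 = 1.12 (mean 1, k 0.25) to √5 = 2.24 (mean 4, k 1), with about 2% more for the t quantile. When they do not differ, the intervals are slightly conservative, at about 96%.

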## 4.2 Power consideration

In this study, a total of 66 patients (allocated in a 2:1 ratio: immunoabsorption (IA) group: 44 patients vs. sham group: 22 patients) will be included. Limited data from 2 small pilot studies, investigating IA in 10 patients with CFS/ME, is available to date. Consequently, data is lacking about precise effects, clinical outcomes, and effect sizes in this group of patients.

The justification of the sample size is based on the primary endpoint (change from baseline of the Chalder Fatigue Scale). The Chalder Fatigue Scale measures fatigue in patients using the overall score (range from 0 to 33) derived from a questionnaire with 11 questions (each scored from 0 to 3, see (Cella & Chalder, 2010; Chalder et al., 1993) for more details). Based on Cella & Chalder 2010, the mean score in a population of patients

suffering from CFS is 24.4 (with a standard deviation of 5.8) and for a healthy sample a mean value of 14.2 (with a standard deviation of 4.6) was observed. A difference of 10 points cannot be expected in this study since only patients suffering from CFS are included. In the systematic review of Nordin et al. 2016 a minimal important difference for the global change ranges between 2.3 and 3.3.

In an earlier study (Cleare et al. 1999) examining the efficacy of various treatments for CFS/ME, the difference in means of the Chalder Fatigue Scale was 4.5 points (Likert score) between the active and the control group. However, no sham-controlled study evaluating the effect of IA on CFS/ME has been conducted so far, but first pilot studies suggest a positive effect of IA in patients with CFS/ME.

To explore the expected precision obtained from the planned study, the distance from the mean group difference of the primary endpoint (change from baseline in Chalder Fatigue Scale) to the limits is calculated using its 95% confidence interval (CI) and a common standard deviation of 5.8 as provided for patient with CFS/ME in (Cella & Chalder, 2010). Using these assumptions and the given group sample sizes of 44 patients and 22 patients, the distance from mean to the limits of the 95%-CI is 3.03 points in the Chalder Fatigue Scale. Assuming an expected drop-out rate of 20% (resulting in expected group sample sizes of 35 and 18 patients, respectively) the distance from the mean to the limits of the 95%-CI increases to 3.37 points in the Chalder Fatigue Scale.

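### Section 9.4 plans only overall person-time AE rate ratios, so harm concentrated in the roughly 10 treatment days would be diluted by about 170 days of follow-up

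*SAP*

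**What the plan says.** Section 9.4 combines descriptive AE summaries by arm with a model: "Incidence rates and 95% confidence intervals (CI) will be calculated using Poisson regression models that consider the different observation periods for each participant". The between-arm comparison follows: "Group comparisons will be made using incidence rate ratios and their 95% CIs". Separate listings of AEs and SAEs, with onset and resolution dates, are also planned, and AEs leading to discontinuation or withdrawal will be highlighted. No period term, no division of person-time and no period-specific rate is mentioned.

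Section 7.3 names the safety endpoint: "Occurrence of treatment emergent adverse events (TEAEs), serious adverse events (SAEs), and discontinuation due to TEAEs".

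Section 4 describes two very different phases. In the first, "Patients will be hospitalized at the clinical site from Day 1 to Day 9 or Day 10 and receive five IA treatments", with venous access by a peripheral line or Shaldon catheter and AE questioning at daily nurse visits. On the planned schedule, "the end of treatment visit (EOT) will take place on Day 10". Afterwards there is no study treatment and there are four scheduled contacts (Days 30, 60, 120 and 180), of which Days 30 and 120 are by telephone. Section 4 adds: "If treatment needs to be terminated, the EOT can occur as early as day 2".

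**The concern.** A rate per unit of observation time summarises a patient's experience well when the underlying rate is roughly constant. Here that is implausible. Procedures, catheter exposure and intensity of questioning all fall sharply at the end of treatment, so both true risk and ascertainment probably fall with them.

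The main consequence is dilution. Treatment-related events enter a ratio whose denominator is almost entirely follow-up time and whose numerator also holds follow-up events that may not differ between arms. A clear excess during the procedures could then look small. A secondary consequence arises if withdrawal differs between arms: the arm losing more patients after the inpatient stay keeps proportionally more high-rate days, so its overall rate rises with no true difference.

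Section 9.4 says that even minor group differences will be discussed, so it matters what a ratio of, say, 1.1 or 1.4 represents.

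**Working it through.** **The plan's own figure.** The SAP states no AE rate or rate ratio. Its only design figure, in section 4.2, is the half-width of the 95% CI for the Chalder difference, t × 5.8 × √(1/n₁ + 1/n₂). For 44 and 22 patients this gives 3.03, as stated. For 35 and 18 it gives 3.377, stated as 3.37. This matters here only because it shows that the 20% drop-out is applied to both arms (44 to 35, 22 to 18).

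**Inputs from the SAP.** Treatment lasts about 10 days and follow-up runs to Day 180, so about 170 days remain. Treatment share of a completer's time: 10/180 = 5.6%. Planned allocation is 44 to 22.

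**Assumed inputs, not in the SAP.** Inpatient rate r₁ = 0.1, 0.2 or 0.3 AEs per day; follow-up rate r₂ = 0.01 per day; withdrawals at Day 10 unless stated otherwise.

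**Formula.** With withdrawal fraction d and true treatment-period ratio R (R = 1 for sham):

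arm rate = (10·r₁·R + (1 − d)·170·r₂) / (10 + (1 − d)·170)

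**Dilution (R = 2 during treatment, no effect in follow-up).** With 20% withdrawal in both arms the denominators are equal (10 + 136 = 146 days) and cancel:

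| r₁ | IA events per patient | Sham events per patient | Overall ratio |
|---|---|---|---|
| 0.1 | 2.00 + 1.36 = 3.36 | 1.00 + 1.36 = 2.36 | 1.42 |
| 0.2 | 4.00 + 1.36 = 5.36 | 2.00 + 1.36 = 3.36 | 1.60 |
| 0.3 | 6.00 + 1.36 = 7.36 | 3.00 + 1.36 = 4.36 | 1.69 |

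With complete follow-up and a wider grid (r₁ 0.05 to 0.20, r₂ 0.005 to 0.02) the ratio runs from 1.13 to 1.70. If the background rate were the same in both periods it would be (20 + 170)/180 = 1.06. If the ratio of 2 held in both periods, the overall ratio would be 2.00, with no dilution.

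**Withdrawal (R = 1, no true effect).**
- 20% in both arms: 1.00.
- 20% IA, 0% sham: (2.36/146)/(2.70/180) = 1.08 at r₁ = 0.1; (4.36/146)/(4.70/180) = 1.14 at r₁ = 0.3.
- 0% IA, 20% sham: 0.93 and 0.87.
- 20% IA, 0% sham, withdrawals spread evenly over follow-up (those leaving contribute half of the 170 days, so 10 + 0.9 × 170 = 163 days): (2.53/163)/(2.70/180) = 1.03 and (4.53/163)/(4.70/180) = 1.06.
- Equal rates in both periods: 1.00, whoever leaves.

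**Precision.** Simple Poisson limits are exp(ln ratio ± 1.96·√(1/E₁ + 1/E₂)), without overdispersion. For the doubling with 20% withdrawal in both arms:
- r₁ = 0.1: expected events 44 × 3.36 = 147.8 and 22 × 2.36 = 51.9, giving 1.42 (1.04 to 1.95).
- r₁ = 0.3: 323.8 and 95.9 events, giving 1.69 (1.34 to 2.12).

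**After a split at Day 12.** Days 11 and 12 take the follow-up rate. With the same doubling and withdrawal, the first-period ratio is 2.016/1.016 = 1.98 at r₁ = 0.1 and 6.016/3.016 = 1.99 at r₁ = 0.3. The follow-up ratio is 1.00.

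**Why not split at each patient's EOT.** Assume 0.3 AEs per day on Days 1 and 2, 0.1 on Days 3 to 10, identical arms, and 20% of IA patients but no sham patients with EOT on Day 2. Up to EOT, the IA rate is (0.6 + 0.8 × 0.8)/(2 + 0.8 × 8) = 1.24/8.4 = 0.148. The sham rate is 1.40/10 = 0.140. The ratio is 1.05 with no true difference, so the individual EOT would bring back the same kind of distortion.

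**The case against.** Allowing for observation time is not an error, and a whole-study rate ratio answers a legitimate question. That stands, and it is why the overall ratio should be kept. Dilution is a matter of what is estimated. It needs the excess to be concentrated in the treatment period, and in the example above the diluted excess would still show, since both intervals exclude 1. That the SAP intends one rate over the whole study is also an inference: it does not say so, but it plans no other rate. The listings would let a reader see clustering in 66 patients, although they give no between-arm estimate for the treatment period.

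Three stronger readings are tempting, and the SAP does not support them.

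- **That the ratio is driven by who withdraws early.** Section 4.2 applies the same 20% to both arms, which gives exactly 1.00 under no effect. The shift needs an imbalance that the document does not project. It roughly halves if withdrawals are spread over follow-up, and it is small against the interval: 1.08 (0.78 to 1.48) and 1.14 (0.90 to 1.45).
- **That AE questioning at baseline in Table 1 contradicts the treatment-emergent endpoint in 7.3.** Asking early is data collection. The endpoint is restricted to treatment-emergent events, the safety set requires at least one cycle, and a detailed window is commonly left to the protocol.
- **That the treatment-period ratio should be the main safety comparison.** This is a preference. The SAP measures immunoglobulins after EOT and restricts live vaccines until 12 weeks after treatment, so later events matter too.

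**Conclusion.** The point holds as a cheap improvement, not as an error in the model. With no period term, the planned ratio would report a true treatment-period doubling as 1.42 to 1.69 under the assumed rates with equal 20% withdrawal, and as 1.13 to 1.70 over the wider grid with complete follow-up. This rests on assumed AE rates, on a higher rate in hospital than afterwards (which the design makes likely but the documents do not quantify), and on an excess confined to the treatment period. Distortion by withdrawal is secondary and conditional: about 1.08 to 1.14 for 20% against 0% leaving at Day 10, less if withdrawals are spread out, and none if they are equal and there is no effect.

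**What to change.** In section 9.4, keep the overall rate ratio and add AE and SAE rates and IA/sham ratios for two periods. Start each patient's person-time at the first procedure and split it at one fixed study day that covers the planned treatment window, for example Day 12, the end of the usual EOT range. Do not split at the individual EOT. Include period and treatment-by-period in the Poisson model, and report both periods without ranking one above the other. Because section 4 allows cycles to be postponed, state that any procedure after the split day is counted where it falls, and report how many there were.

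The cost is some SAP wording and one division of person-time; onset dates are already planned for the listings. The downside is precision. In the r₁ = 0.1 doubling example the first period holds about 88.7 and 22.4 expected events, giving 1.98 (1.25 to 3.16) against 1.42 (1.04 to 1.95) overall. Nor does the split remove every effect of withdrawal: if 20% of IA and no sham patients left at Day 10, the first-period ratio under no effect would be (1.016/11.6)/(1.02/12) = 1.03.

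### The only between-arm safety comparison in SAP 9.4, a Poisson rate ratio with 95% CI, gives no usable estimate if an arm has no event, and no fallback is specified

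*SAP*

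**What the plan says.** Section 7.3 of the SAP lists as safety endpoints: "Occurrence of treatment emergent adverse events (TEAEs), serious adverse events (SAEs), and discontinuation due to TEAEs". Section 9.4 opens with description: "Descriptive methods will be used for analysis of safety parameters, adverse events and their intensity in total and reported separately for the intervention groups". It then gives its one model-based method: "Incidence rates and 95% confidence intervals (CI) will be calculated using Poisson regression models that consider the different observation periods for each participant". The comparison follows: "Group comparisons will be made using incidence rate ratios and their 95% CIs".

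Section 9.4 also plans individual listings: "A comprehensive listing of all individual patient adverse events (AEs) and severe adverse events (SAEs) will be presented". In these, "any AEs leading to study drug discontinuation or study withdrawal will be specifically highlighted". It adds that results will be discussed even where arm differences are small, because significance is not the aim.

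The arm sizes are in section 4.2: "allocated in a 2:1 ratio: immunoabsorption (IA) group: 44 patients vs. sham group: 22 patients". Section 11 names R as the software. The SAP does not state the type of interval (Wald, profile likelihood or exact), what to do when an arm has no event, or an expected rate for SAEs or discontinuations.

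**The concern.** SAEs and discontinuations are usually few, and the sham arm has 22 patients. A Poisson model estimates the log rate in each arm. With no event in an arm, that estimate has no finite value, and neither has the log rate ratio. The standard error that software then prints reflects where the iterations stopped, not the data.

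The safety pattern of most interest is several events under immunoadsorption and none under sham. There the one planned comparison would return an interval that excludes nothing, and the sham rate would have no usable upper limit. This would happen even if every count were truly Poisson and correctly defined.

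**Working it through.** **Inputs.** Arm sizes 44 and 22 (SAP 4.2). Follow-up to Day 180 (SAP 4), taken as complete for all patients. The SAP gives no event rate, so 0.02, 0.05 and 0.10 expected events per patient over follow-up are assumptions, equal in both arms.

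**The plan's own figure.** There is none for safety. The only figure built on these arm sizes is the 3.03-point half-width in 4.2, which reproduces: t(0.975; 64) × 5.8 × √(1/44 + 1/22) = 3.03.

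**Step 1: how often an arm is empty.** With rate λ per patient:
- P(no sham event) = exp(−22λ)
- P(no sham event and at least one active event) = exp(−22λ) × [1 − exp(−44λ)]

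| λ | No sham event | No sham event, at least one active event |
|---|---|---|
| 0.02 | exp(−0.44) = 64% | 38% |
| 0.05 | exp(−1.10) = 33% | 30% |
| 0.10 | exp(−2.20) = 11% | 11% |

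An empty sham arm is more likely than not only if λ is below ln 2 / 22 = 0.032.

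**Step 2: what the planned model returns.** For x active and y sham events, the Wald standard error of the log rate ratio is √(1/x + 1/y), which has no limit as y goes to 0. Fits with a log person-time offset bear this out:
- 10 against 0: log rate ratio 22.1, SE about 17,000, p = 0.999, interval 0 to infinity.
- 3 against 0 and 8 against 0: SE about 11,500, p = 0.999, interval 0 to infinity.
- R's glm stops its iterations earlier and gives SE about 3,314 and p about 0.996 for 3, 5 and 8 against 0, again with interval 0 to infinity. R's default profile-likelihood routine stopped with an error on these fits.

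**Step 3: what the same counts can support.** Given the total, the active count is binomial. For x against 0, the exact lower 95% limit for the rate ratio is p/(1 − p) × 22/44, with p = 0.025^(1/x). The profile-likelihood lower limit has the same form, with p = exp(−3.841/(2x)).

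| Events, active against sham | Exact lower limit | Profile lower limit |
|---|---|---|
| 3 against 0 | 0.21 | 0.56 |
| 6 against 0 | 0.59 | 1.33 |
| 8 against 0 | 0.85 | 1.84 |
| 10 against 0 | 1.12 | 2.36 |

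The upper limit is infinite in every row. In the other direction, 0 against 2 gives an exact upper limit of 2.66.

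For an empty sham arm, the exact upper limit of the rate is 3.69 / (22 × 180/365.25) = 0.34 events per patient-year, or 3.69/22 = 0.17 per patient over 180 days.

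**Step 4: patients with at least one event.** The risk difference with Newcombe's interval, built from Wilson score limits, stays finite:
- 3/44 against 0/22: 6.8% (95% CI −8.7 to 18.2)
- 5/44 against 0/22: 11.4% (−4.8 to 24.0)
- 8/44 against 0/22: 18.2% (1.0 to 32.0)

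In the last case the planned model gives p of 0.996 or more, while the risk-difference interval excludes 0.

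**The case against.** The strongest reply is that section 9.4 does not rest on the model alone. It plans descriptive reporting by arm, lists every event with its arm, highlights events leading to discontinuation, and plays down significance. In a single-centre exploratory trial of 66 patients, 6 SAEs against 0 would be seen. This stands. A reader might infer that serious harm would be hidden or misreported; the same section shows otherwise. What fails is the comparative estimate and its interval.

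Three further replies stand in part:
- **Likelihood.** A reader might infer that an empty sham arm is to be expected. The SAP gives no rate to support that. The background section calls the procedure generally well tolerated, which makes low rates plausible but fixes no number.
- **Interval type.** A reader might infer that the plan prescribes the Wald interval. It says only 95% CI, and a profile-likelihood interval would have a finite lower limit. But leaving the choice open has a cost: for 6 or 8 against 0 the profile limit is above 1 and the exact limit below it, so a choice made after seeing the counts could decide the message.
- **Scope.** The Poisson sentence does not name SAEs or discontinuations. That it covers them is an inference, since 9.4 offers no other comparison. If the models for secondary endpoints in 9.3 applied instead, a logistic model would fail in the same way, through separation. On that reading, frequencies and percentages by arm are already planned, and that part of the fix only confirms them.

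It is also true that the exact ratio interval still includes 1 for 3, 6 and 8 against 0. It nevertheless separates these cases from each other and from 10 against 0, which the Wald interval cannot do.

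**Conclusion.** The point holds as a gap in the stated method. Section 9.4 relies on a rate ratio that has no finite, non-zero estimate when one arm has no event, and it gives neither an interval type nor a rule for that case. At assumed rates of 0.02 to 0.10 events per patient, the chance of an empty sham arm runs from 64% down to 11%. The chance of an empty sham arm with at least one active event runs from 38% to 11%. These figures rest on equal rates in both arms, full follow-up and Poisson counts.

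The documents support neither that such an outcome is likely nor that an imbalance would go unreported. They support that the promised between-arm estimate would carry no information in a plausible case. The plan should be changed before the counts by arm are known.

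**What to change.** In section 9.4, keep Poisson regression for total adverse events. For SAEs, discontinuations due to TEAEs and other sparse categories, add:
- exact Poisson (Garwood) 95% CIs for each arm's rate;
- an exact conditional 95% CI for the rate ratio, with person-time as exposure;
- the number and percentage of patients with at least one event per arm, and the risk difference with a score-type 95% CI such as Newcombe's.

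Name the sparse categories in advance. At the least, state that these methods apply whenever an arm has no event. Naming them is cleaner, because the method then does not depend on the observed counts.

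The cost is a few sentences and a few lines of R (poisson.test gives the rate and rate-ratio intervals), with no new data. The downside is that exact intervals are somewhat conservative and do not account for repeat events within a patient; the comparison of patients with at least one event covers the latter. This changes the analysis only and proposes no clinical rule.
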